Appendix 1.3. Example of SAS Code for Calculating Percent Reduction in Mean ABR

```
proc genmod data=main;
class trt subjid;
model bleeds = trt /offset=lyears dist=negbin link=log alpha=0.05;
** offset=log of years **;
repeated subject=subjid/ Type=UN;
estimate 'log diff' trt 1 -1 / exp;
ods output estimate=ci_ratio;
run;

data ci_reduction;
set ci_ratio;
where Label= "Exp(log diff)";
Percent_reduction = (1- LBetaEstimate)*100;
Lower_bound = (1- LBetaUpperCL)*100;
Upper_bound = (1- LBetaLowerCL)*100;
run;
```

Appendix 1.4. Additional US-specific Analyses

Total ABR:

Supplementary analysis: Repeat the same analysis model and summary for the main analysis as described in [Section 6.1.1.1](#) on the Total ABR from Week 12 through data cutoff using the ‘Dosed’ population regardless of the length of follow-up preinfusion or postinfusion. In addition, the imputation rule per given event below in Table 10 will be applied.

Table 10. Imputation Rules for US-Specific Analysis of Total ABR

Event	Imputation Rule
Resumption of prophylaxis regimen	The Total ABR post prophylaxis resumption date through data cutoff will be imputed with 35.
Taking FVIII infusions post PF-07055480 infusion for a time period in a manner similar to prophylaxis regimen (Note: these events will be identified based on clinical review.)	The Total ABR during this period will be imputed with 35.

If a participant resumes prophylaxis regimen and then later discontinues from the study prior to data cutoff, his Total ABR post prophylaxis resumption data through data cutoff will be imputed with 35 (i.e., the imputation rule will be applied for the period from study discontinuation to data cutoff).

The corresponding supplementary estimand is the treatment effect of PF-07055480 compared to routine prophylaxis with respect to Total ABR (treated and untreated bleeds) after prior prophylaxis treatment is stopped following infusion, from Week 12 [Day 78] through data cutoff.

Table 11. Supplementary Estimand of Total ABR

Estimand Attribute	Description
Population	Male participants ≥ 18 years of age with moderately severe to severe hemophilia A (FVIII:C $\leq 1\%$), who have tested negative for anti-AAV6 nAb and have no medical history of FVIII inhibitor.
Variable	Total ABR (treated and untreated bleedings) from Week 12 [Day 78] through data cutoff post PF-07055480 infusion.
Intercurrent Event	
 • Data post prophylaxis resumption date through data cutoff will be imputed. • Data during a time period when the participant was taking FVIII infusion in a manner similar to prophylaxis regimen will be imputed. • Data after study discontinuation will not be imputed unless prophylaxis was resumed prior to discontinuation.

Estimand Attribute	Description
Population-Level Summary	Total ABR post PF-07055480 infusion will be compared to participants' Total ABR on prior FVIII prophylaxis regimen using a repeated measure negative binomial regression model. Model-based estimated difference in mean Total ABR and the 95% CI will be reported. In addition, percent reduction in mean Total ABR and the corresponding 95% CI will be estimated.

A sensitivity analysis to repeat the same analysis model and summary as described in [Section 6.1.1.1](#) on the Total ABR from Week 12 through at least 15 months (up to data cutoff) using the 'Efficacy' population and apply the imputation rules described above.

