10.7. Appendix 7: Factor Replacement Regimens and Bleed Definitions

Definition of Factor Replacement Regimens

Prophylaxis Therapy: The regularly scheduled and regimented administration of factor replacement therapy to prevent bleeding.

Preventative Therapy: Infusion of clotting factor that is given in anticipation of a planned physical activity that has a high risk of injury (eg, surgery or sporting activity).

On-Demand Therapy: The administration of factor replacement therapy only at the time of an acute bleeding event.

Definition of a Bleed

Treated Bleed: An event necessitating administration of coagulation factor within 72 hours of signs or symptoms of bleeding (protocol definition, unless specifically referring to untreated bleed).

Untreated Bleed: A bleeding event not necessitating administration of coagulation factor within 72 hours of signs and symptoms of bleeding.

New Bleed: A bleed occurring >72 hours after stopping treatment from the original bleed for which treatment was initiated or a bleed occurring at a different site from the original bleed regardless of the time from last injection.

Definition of a Bleed Location

Target Joint: Defined as a major joint (eg, hip, elbow, wrist, shoulder, knee, and ankle) into which repeated bleeds occur (3 or more spontaneous bleeds into a single joint within a consecutive 6-month period). A target joint is considered resolved when there are ≤ 2 bleeds into the joint within a 12-month period.

Joint Bleed: A bleeding episode characterized by rapid loss of range of motion as compared with baseline that is associated with any combination of the following: pain or an unusual sensation in the joint, palpable swelling, and warmth of the skin over the joint.

Muscle Bleed: An episode of bleeding into a muscle, determined clinically and/or by imaging studies, generally associated with pain and/or swelling and functional impairment.

Definition of Bleed Types

Spontaneous Bleeds: Bleeding for no apparent/known reason particularly into the joints, muscles, and soft tissues.

Traumatic Bleeds: Bleeding event occurring for an apparent/known reason.

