2.2.1. Primary Estimand

The primary estimand is the treatment effect of PF-07055480 compared to routine prophylaxis with respect to Total ABR (treated and untreated bleeds) after prior prophylaxis treatment is stopped following infusion, from Week 12 [Day 78] through at least 15 months (up to data cutoff) postinfusion.

The corresponding estimand attributes are provided in Table 3 below.

Table 3. Attributes of Primary Estimand

Estimand Attribute	Description
Population	Male participants ≥ 18 years of age with moderately severe to severe hemophilia A (FVIII:C $\leq 1\%$), who have tested negative for anti-AAV6 nAb and have no medical history of FVIII inhibitor.
Variable	Total ABR (treated and untreated bleedings) from Week 12 [Day 78] through at least 15 months (up to data cutoff) post PF-07055480 infusion.
Intercurrent Event	
 • Any data after the resumption of FVIII prophylaxis regimen (if necessary) will be excluded. • Data after study discontinuation will not be imputed.
Population-Level Summary	Total ABR post PF-07055480 infusion will be compared to participants' Total ABR on prior FVIII prophylaxis regimen using a repeated measure negative binomial regression model. Model-based estimated difference in mean Total ABR and the 95% CI will be reported. In addition, percent reduction in mean Total ABR and the corresponding 95% CI will be estimated.

Because no more than a single dose of study intervention will be administered during the study, there should be no treatment discontinuations. If it is determined by the investigator that a participant should resume routine prophylaxis post PF-07055480 infusion, date and

reason of investigator decision to resume FVIII prophylaxis will be collected in the eCRF, and this date will be considered as the date of FVIII prophylaxis resumption.

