Cumulative follow up through 5 years postinfusion	Day 78 to End of the study

For participants with incomplete data for the entire yearly time period, including participants who discontinued, all data during the specified period will be annualized and summarized utilizing the number of days of follow-up during the given time period (i.e., observation period). Total ABR for each participant will be calculated as below:

Total ABR =

$$\frac{(\text{Number of treated and untreated bleeding episodes during the given time period}) \times 365.25}{(\text{Number of days of follow-up in the given time period})}$$

Data before Week 12 postinfusion are excluded to account for the potential differences in participants' pharmacokinetics postinfusion. As a result, the denominator in the above calculation for the Month 15 and cumulative follow-up intervals will be [the last date in the given time period – (Date of PF-07055480 infusion) – 77 days +1].

For the primary endpoint assessment of Total ABR from Week 12 through at least 15 months (up to data cutoff), the number of bleeds post resumption of prophylaxis regimen or study discontinuation will be excluded. As a result, the denominator (i.e., number of days in the observation period) in the above Total ABR calculation will include days up to data cutoff, the day before resumption of prophylaxis regimen, or discontinuation date, whichever occurs earliest.

Total ABR during yearly intervals and cumulative follow-up intervals are considered as secondary endpoints. If the participant discontinues from study before the end of the prespecified observation period, the last date in the given observation period will be the date of study discontinuation. In addition, if FVIII prophylaxis regimen is resumed for a participant as defined in Protocol Section 6.5.1 then data collected on and after the date of prophylaxis resumption entered in the eCRF by the investigator will be excluded from the calculation of Total ABR by interval, which means the bleeding events will be excluded and the corresponding time period will be deducted as well.

Total ABR prior to PF-07055480 will be calculated using all treated and untreated bleeds documented during the lead-in study (C0371004) up to preinfusion of PF-07055480 and the respective number of days of follow-up within the lead-in study and preinfusion period using the same formula presented above.

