Appendix 2. Summary of Efficacy/PRO Analyses

Endpoint	Analysis Type	Population	Data Inclusion and Rules for Handling Intercurrent Events and Missing Data	Analysis
Total ABR (from Week 12 through at least 15 months [up to data cutoff] postinfusion of PF-07055480)	Primary analysis: main analysis	Efficacy	
 Any data after the resumption of FVIII prophylaxis regimen (if necessary) will be excluded. Data after study discontinuation won't be imputed. 	A generalized linear model with repeated measures with negative binomial distribution and identity link function to demonstrate non-inferiority to prior FVIII prophylaxis regimen with a NI margin of 3.0 bleeds/year. If noninferiority is demonstrated, further testing for superiority would be conducted.
Total ABR (from Week 12 through data cutoff postinfusion of PF-07055480)	Primary analysis: sensitivity analysis	Dosed	Same as for the main analysis.	Same as above but no hypothesis testing.
Total ABR (from Week 12 through data cutoff postinfusion of PF-07055480)	Primary analysis: sensitivity analysis	Evaluable	Same as for the main analysis.	Same as above but no hypothesis testing.
Total ABR postinfusion (from Week 12 through at least 15 months [up to data cutoff] postinfusion of PF-07055480) compared to separately the first and the latest 6 months preinfusion data	Primary analysis: sensitivity analysis	Efficacy	Same as for the main analysis. To include the bleeding data collected during only the latest 6 months and the first 6 months separately during the lead-in study up to preinfusion of PF-07055480 in the 'Efficacy' population.	Same as above but no hypothesis testing.
Total ABR postinfusion (from Week 12 through at least 15 months [up to data cutoff] postinfusion of PF-07055480)	Primary analysis: sensitivity analysis	Efficacy	Same as for the main analysis. Include only the data collected in the lead-in study (C0371004) and the data postinfusion of PF-07055480 in the 'Efficacy' population.	Same as above but no hypothesis testing.

Endpoint	Analysis Type	Population	Data Inclusion and Rules for Handling Intercurrent Events and Missing Data	Analysis
compared to the data collected in the lead-in study.				
Total ABR postinfusion (from Week 12 through data cutoff postinfusion of PF-07055480) with imputation	US-specific analysis	Dosed	Same as for the main analysis and the imputation rules described in Table 10 will be applied.	Same as for the main analysis with hypothesis testing.

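### Prophylaxis-like FVIII use without a recorded resumption counts as PF-07055480 time in the main Total ABR and Treated ABR analyses; only the US-specific Total ABR analyses handle it

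*SAP*

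**What the plan says.** **Main analyses.** For the primary Total ABR estimand (SAP 2.2.1, Table 3) the resumption rule is: "Any data after the resumption of FVIII prophylaxis regimen (if necessary) will be excluded". The date comes from the investigator's decision in the eCRF, and "this date will be considered as the date of FVIII prophylaxis resumption". The day count runs to data cutoff, "the day before resumption of prophylaxis regimen, or discontinuation date, whichever occurs earliest" (SAP 3.1.1). SAP 2.2.2, Table 5 handles Treated ABR the same way.

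**US-specific analyses.** SAP Appendix 1.4, Table 10 has two rows. One is resumption. The other is "Taking FVIII infusions post PF-07055480 infusion for a time period in a manner similar to prophylaxis regimen", identified by clinical review, for which "The Total ABR during this period will be imputed with 35". This is run on the Dosed population, and an Efficacy-population repeat is to "apply the imputation rules described above". Both cover Total ABR only. Appendix 2 describes each as "Same as for the main analysis with hypothesis testing".

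**Treated ABR.** SAP 6.2.2.2 plans Dosed and Evaluable repeats plus interval analyses, and rules out any others.

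**Definition.** Protocol Appendix 7 defines prophylaxis by its pattern: "The regularly scheduled and regimented administration of factor replacement therapy to prevent bleeding".

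**The concern.** By giving the event its own row in Table 10, the sponsor accepts that a participant can take FVIII in a prophylaxis-like way with no resumption on record. In the main analyses that participant's covered time stays in both the bleed count and the day count as time on gene therapy. Another participant with the same infusion pattern and a completed form is cut off at the form date. The handling turns on an eCRF entry, although the protocol defines prophylaxis by how FVIII is given.

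If the participants who do this are those whose gene therapy is failing, exogenous FVIII lowers their bleeding and the postinfusion ABR looks better than gene therapy alone would give. Noninferiority is then easier to declare in the situation where the test should guard against it.

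Treated ABR is the more exposed endpoint. Under SAP Table 6, a bleed not logged as treated is untreated even if FVIII was infused within 72 hours, so a bleed covered by a routine infusion can drop out of Treated ABR altogether.

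A second weakness is identification. The clinical review has no stated frequency, duration or masking criterion, and the study is open-label.

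**Working it through.** **1. The plan's own figures.** Protocol 9.2 gives Total ABR 5 before and 2 after infusion, margin 3, 50 participants, correlation 0.2, one-sided alpha 0.025 and power of at least 95%. Margin: 16.8 × 1.17 = 19.66, and 1 − 3/19.66 = 84.7% preserved, as stated. Power was simulated with the SAP model (identity-link negative binomial GEE, robust SE), 0.5 years before infusion and Day 78 to Day 455 after it (378 days, 1.035 years). The dispersion is not given, so 0.5 to 5 was tried. Power was 98.8% to about 100%. The stated figure reproduces.

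**2. Handling, side by side.**

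| Exposure | Main Total ABR | Main Treated ABR | US-specific Total ABR |
|---|---|---|---|
| Recorded resumption | excluded | excluded | scored 35 |
| Prophylaxis-like use, not recorded | kept | kept | scored 35 |

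**3. One participant (illustration).** Four bleeds in 4 months, then 16 months of regular FVIII with none. Kept: 4/(20/12) = 2.4 bleeds/year. Covered time excluded: 4/(4/12) = 12 bleeds/year.

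**4. At the noninferiority boundary.** Assumptions: 50 participants; 5/year before and 8/year after infusion, so the true difference is 3.0; dispersion 0.5; 0.6-1.5 years before and 1.03-2.5 years after infusion; half of bleeds spontaneous. Some participants start regular FVIII two weeks after a third spontaneous bleed. The share affected and the cut in bleeding are varied. Two figures in a cell are separate runs (3,000 and 1,500 trials); a dash means not reported.

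| Affected | Cut in bleeding | Estimate, kept | NI error, kept |
|---|---|---|---|
| none | – | – | 3.7%, 2.7% |
| about 8% | 75% (8 to 2) | 2.64, 2.67 | 7.0%, 7.5% |
| about 8% | 37.5% (8 to 5) | 2.79 | 6.3% |
| about 19% | 75% | 2.16, 2.08 | 16.6%, 18% |
| about 19% | 50% | – | 12% |
| about 19% | 37.5% | 2.59 | 7.8% |
| about 19% | 25% | – | 6% |

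Excluding the covered periods gave estimates of 2.97 to 3.05 and error of 4-5%, close to the result with no such use.

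**5. At the planned rates.** With covered share p of postinfusion time and covered rate r, keeping the time shifts the difference by p × (r − 2) relative to exclusion.
- p = 5%: −0.10 (r = 0) to +0.15 (r = 5).
- p = 10%: −0.20 (r = 0) to +0.30 (r = 5), that is −3.20 to −2.70 against −3.0.

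When use is triggered by bleeding as in step 4, few participants reach the trigger at 2/year. The shift is then at most about 0.1 and noninferiority is unaffected.

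**6. Leverage of the clinical review.** One participant of 50 flagged for the whole window moves the US-specific mean by (35 − 5)/50 = 0.60 to (35 − 0)/50 = 0.70 bleeds/year. At the planned rates the US-specific difference is −3 + 33p. It reaches 0 at p = 3/33 = 9.1% and the margin of 3 at p = 6/33 = 18.2%.

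**The case against.** The strongest reply is that Total ABR is already covered. SAP 6.1.1.2 points to Appendix 1.4, which prespecifies two analyses of this event, and scoring at 35 is harsher than exclusion. That stands for Total ABR as a robustness check. It does not change the primary estimate, and it leaves Treated ABR with nothing.

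A second reply is that most such participants would be recorded. Protocol 6.5.1 lists three or more spontaneous bleeds among the conditions under which prophylaxis may be resumed, and the medical monitor is to be informed. Infusion reasons are entered in the eDiary, which is reviewed at visits. This makes long unrecorded periods less likely, and no document gives their frequency. But resumption is permitted rather than automatic, and Table 10 itself allows for the unrecorded case.

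Some stronger readings are tempting and not supported:
- That the plan contradicts its primary estimand. The supplementary estimand in Appendix 1.4 uses the same phrase about prior prophylaxis being stopped, with different handling, so the phrase fixes no strategy.
- That keeping the time always favours gene therapy. Against scoring at 35 it does whenever the covered rate is below 35. Against exclusion it does so only when the covered rate is below the uncovered one; step 5 shows the reverse.
- That noninferiority error reaches 20%. Errors near that level need a 75% cut, which takes informal FVIII to 2/year when simulated prophylaxis runs at 5/year.
- That superiority error is inflated. It was not computed, and ABR superiority comes at steps 6 and 7 of Table 8, after AIR and FVIII consumption, which count every infusion.
- That the clinical review affects the primary Type I error. The US-specific tests lie outside Table 8.

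**Conclusion.** The gap is real and narrow. The same exposure is excluded when recorded and kept when not, and Treated ABR has no analysis that shows the effect.

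At the noninferiority boundary, with about 7-19% of participants affected, keeping the time turns a true difference of 3.0 into an estimate of about 2.1 to 2.8, with noninferiority error of about 6-18%. The baseline in the same simulations is about 3-4%, so not all the excess over 2.5% comes from this point. These figures rest on the assumed frequency, the size of the bleeding reduction, the dispersion and the within-participant correlation; the documents do not give the first three for this setting.

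If the drug performs as planned, the effect is negligible. This is a cheap improvement in consistency, and it does not show that the primary analysis is invalid.

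**What to change.** 1. In SAP 2.2.1, 2.2.2 and 3.1.1, remove the bleeds and the days of each flagged period from the main Total ABR and Treated ABR analyses, as is done for bleeds and days after a recorded resumption. Remove only the flagged period. Table 10 speaks of a time period, and ending observation at its start would discard valid later time and bleeds. At minimum, add this exclusion as a prespecified sensitivity analysis in 6.1.1.2 and, above all, in 6.2.2.2.
2. Replace the open clinical review with an algorithm on eDiary infusion dates and reasons: infusions not given for a bleed or surgery, at a stated frequency for a stated duration. Fix it before database lock, apply it without sight of bleed counts, and use it for Appendix 1.4 too.

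Cost: SAP wording and one more programmed data cut, since Appendix 1.4 already needs the flagged periods. Changing the main analysis also needs a matching line in Protocol sections 3 and 9.1.1. The downside is slightly less postinfusion time and possibly a less favourable ABR.

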7.2. Participant Discontinuation/Withdrawal from the Study

A participant may withdraw from the study at any time at his/her own request, or may be withdrawn at any time at the discretion of the investigator for safety, behavioral, compliance, or administrative reasons. Reasons for discontinuation from the study include the following:

Refused further follow-up;

Lost to follow-up;

Death;

Study terminated by sponsor.

At the time of discontinuing from the study, if possible, an early discontinuation visit should be conducted, as shown in the SoA. See the SoA for assessments to be collected at the time of study discontinuation and follow-up and for any further evaluations that need to be completed.

The early discontinuation visit applies only to participants who are enrolled/randomized and then are prematurely withdrawn from the study. Participants should be questioned regarding their reason for withdrawal.

If a participant withdraws from the study, he/she may request destruction of any remaining samples taken and not tested, and the investigator must document any such requests in the site study records and notify the sponsor accordingly.

If the participant withdraws from the study and also withdraws consent (see Section [7.2.1](#)) for disclosure of future information, no further evaluations should be performed and no additional data should be collected. The sponsor may retain and continue to use any data collected before such a withdrawal of consent.

When a participant withdraws from the study because of an SAE, the SAE must be recorded on the CRF and reported on the CT SAE Report.

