Based on the simulations described above, the sample size for the primary analysis based on Total ABR remains unchanged. A sample size of at least 50 dosed participants who have completed at least 15 months of follow-up post PF-07055480 infusion will provide at least 95% power (1-sided test with alpha=0.025) to demonstrate noninferiority of gene therapy compared to prophylaxis treatment based on a difference in mean Total ABR with an NI margin of 3.0 bleeds/year.

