3.2.4. FVIII Activity Level from Week 12 through 15 Months Postinfusion

The beginning of steady state will be considered as Week 12 for analysis purposes within this Phase 3 study. Additionally, the data from this Phase 3 study will be utilized to confirm the timing of the onset of steady state.

The Factor VIII activity from Week 12 through 15 months postinfusion will be calculated for each participant as a geometric mean of all appropriate FVIII activity measures (including unscheduled visit observations) from Week 12 through 15 months (up to the upper bound of the Month 15 visit window: Week 67) after PF-07055480 infusion based on central chromogenic assay and one-state clotting assay separately. When multiple appropriate FVIII activity observations are collected on the same day for a participant, the average level of these observations will be used for that given day. FVIII activity will be imputed with 0.9% after the participants have resumed prophylaxis regimen up to data cutoff or Week 67, whichever occurs earlier.

If a participant has missing data for a study visit or has otherwise discontinued due to any reasons other than lack of efficacy but has not resumed prophylaxis prior to completing the designated follow-up period, all available data will be included to calculate geometric mean despite the missed measurements. Specifically, imputation of FVIII activity will be applied per scenarios listed below:

- Resumed prophylaxis but remained in the study: Impute FVIII activity with 0.9% at any protocol-defined visits post resumption of prophylaxis until data cutoff or Week 67, whichever occurs earlier.
- Resumed prophylaxis and then discontinued from the study due to any reasons: Impute FVIII activity with 0.9% at any protocol-defined visits post resumption of prophylaxis until data cutoff or Week 67, whichever occurs earlier.
- Discontinued from study due to lack of efficacy but has not resumed prophylaxis: Impute FVIII activity with 0.9% at any protocol-defined visits post study discontinuation until data cutoff or Week 67, whichever occurs earlier.
- Discontinued from the study due to any reasons other than lack of efficacy but has not resumed prophylaxis: No imputation will be applied. FVIII activity after study discontinuation will be considered missing.

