3.2.5. FVIII Activity Level by Visit

Mapping for unscheduled visit observations and exclusion in FVIII activity data are described in [Section 3.2.1](#). FVIII activity analyzed by the central laboratory will be reported for chromogenic assay and one-state clotting assay separately. FVIII activity will be imputed with 0.9% through data cutoff after the participants have resumed prophylaxis regimen and after they discontinued from the study due to lack of efficacy. FVIII activity won't be imputed after participants discontinue from the study due to reasons other than lack of efficacy if they have not resumed prophylaxis. Specifically, imputation of FVIII activity will be applied per scenarios listed below:

- Resumed prophylaxis but remained in the study: Impute FVIII activity with 0.9% at any protocol-defined visits post resumption of prophylaxis until data cutoff.
- Resumed prophylaxis and then discontinued from the study due to any reasons: Impute FVIII activity with 0.9% at any protocol-defined visits post resumption of prophylaxis until data cutoff.
- Discontinued from study due to lack of efficacy but has not resumed prophylaxis: Impute FVIII activity with 0.9% at any protocol-defined visits post study discontinuation until data cutoff.
- Discontinued from the study due to any reasons other than lack of efficacy but has not resumed prophylaxis: No imputation will be applied. FVIII activity after study discontinuation will be considered missing.

FVIII activity levels by visit will be summarized. In addition, the percentage of participants with FVIII activity level $\geq 40\%$ will be reported by visit up to data cutoff.

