5. GENERAL METHODOLOGY AND CONVENTIONS

The primary analysis will be conducted when at least 50 dosed participants have completed at least 15 months of follow up post PF-07055480 infusion. The primary analysis is focused on the efficacy and safety during the follow-up through data cutoff postinfusion. The associated efficacy endpoints and analysis methods are listed in the tables below. The final analysis will be conducted when all dosed participants have completed the entire study (i.e., 5 years in follow-up duration per participant) or discontinued prematurely from the study. The planned endpoints after the primary analysis are focused on extended efficacy and longer-term safety. As this is an open-label study, the sponsor may conduct reviews of the data during the course of the study for the purpose of safety assessments. There may be several periodic reviews of data between the primary analysis and the final analysis for the purpose of publications and regulatory updates, etc.

Category of Endpoint	Primary Analysis Endpoints And Statistical Analysis Methods
Primary	Total ABR (treated and untreated bleedings) from Week 12 [Day 78] through at least 15 months (up to data cutoff) postinfusion of PF-07055480 will be compared to preinfusion

Category of Endpoint	Primary Analysis Endpoints And Statistical Analysis Methods
	of PF-07055480 (under SOC FVIII prophylaxis replacement regimen). A repeated measures negative binomial regression model will be used to test NI with NI margin = 3 bleeds/year at the one-sided alpha level = 0.025. If noninferiority is demonstrated, further testing for superiority would be conducted.
Key secondary	
 FVIII activity level > 5% at 15 months postinfusion of PF-07055480. The percentage of participants will be compared to a null hypothesis of percentage $\leq 68\%$ using an exact binomial test at the one-sided alpha level = 0.025. Based on the interim data of the Phase 1b/2 Study, 80% of participants in Cohort 4 (Phase 3 study dose) had a FVIII activity level greater than 5% at 18 months postinfusion. The null hypothesis of percentage $\leq 68\%$ will be rejected if the observed percentage is greater than 80%. Treated ABR from Week 12 [Day 78] through at least 15 months (up to data cutoff) post PF07055480 infusion will be analyzed separately using the same method as applied to Total ABR.

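### The US-specific Total ABR analyses do not penalise a participant who leaves for lack of efficacy without resuming prophylaxis, although other SAP rules count that event as failure

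*SAP*

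**What the plan says.** - **US-specific Total ABR (SAP Appendix 1.4).** Table 10 lists two penalised events: resumption of prophylaxis, and a period of FVIII use that clinical review judges to resemble prophylaxis. Each is charged at 35 bleeds/year. The text below the table carries the 35 through to data cutoff for someone who resumes and later leaves the study. Table 11 gives the general rule for dropouts: "Data after study discontinuation will not be imputed unless prophylaxis was resumed prior to discontinuation". Appendix 2 assigns these analyses hypothesis testing.
- **Main Total ABR (SAP 2.2.1, Table 3).** "Data after study discontinuation will not be imputed". SAP 3.1.1 ends the denominator at cutoff, the day before resumption, or discontinuation, whichever is first.
- **FVIII activity summaries.** SAP 3.2.4 names the event exactly: "Discontinued from study due to lack of efficacy but has not resumed prophylaxis: Impute FVIII activity with 0.9"%. SAP 3.2.5 applies the same value by visit to participants "after they discontinued from the study due to lack of efficacy".
- **FVIII >5% at Month 15 (SAP 2.2.2, 3.2.1 and 6.2.1.1).** Anyone who discontinues before Month 15, for any reason, counts as a failure.
- **Reasons for leaving (Protocol 7.2).** "Reasons for discontinuation from the study include the following": refusal of further follow-up, loss to follow-up, death, and termination by the sponsor. Lack of efficacy is not named.

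**The concern.** The US-specific analyses are the only planned Total ABR analyses that charge loss of efficacy as failure. Within them, two participants whose gene therapy has failed and who then leave are treated in opposite ways. If a resumption decision is on record before exit, 35 bleeds/year runs to cutoff, including time when nobody is observing the participant. If there is no such decision and no prophylaxis-like use, follow-up simply ends.

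The SAP elsewhere accepts that leaving for lack of efficacy is itself a failure event. Appendix 1.4 also accepts imputing over unobserved time after dropout. The omission therefore does not follow from either principle. It favours PF-07055480 whenever such a dropout occurs, and the bleeding and FVIII summaries would then disagree about the same person.

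**Working it through.** **1. The rules side by side, for a failed participant who leaves before Month 15**

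| Analysis | Resumption on record, then leaves | Leaves for lack of efficacy, no resumption, no prophylaxis-like use |
|---|---|---|
| Main Total ABR | truncated at resumption | truncated at exit |
| US-specific Total ABR | 35/year from resumption to cutoff | truncated at exit |
| FVIII geometric mean and by visit | 0.9% | 0.9% |
| FVIII >5% at Month 15 | failure | failure |

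Only the US-specific row separates the two.

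**2. Inputs**

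- Protocol 9.2: n = 50, Total ABR of 5 bleeds/year before and 2 after infusion, correlation 0.2.
- SAP 5: "NI margin = 3 bleeds/year at the one-sided alpha level = 0.025".
- SAP 3.1.1: minimum postinfusion window Day 78 to Day 455, which is 378 days or 1.035 years.
- SAP Table 10: penalty 35/year.
- Preinfusion time 0.5 years, the minimum lead-in.
- Assumptions: the negative binomial dispersion k is not stated, so a range is used. The dropout is taken to bleed at 2/year before exit unless noted.

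**3. The plan's own figure**

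For its target of 50, Protocol 9.2 says the design "will provide at least 95% power (1-sided test with alpha=0.025) to demonstrate noninferiority of gene therapy compared to prophylaxis treatment". As a check, power = Φ((3 − (2 − 5))/SE − 1.96), with SE² = (v0 + v1 − 2·0.2·√(v0·v1))/50 and v = μ/t + kμ².

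At k = 4: v0 = 5/0.5 + 4·25 = 110 and v1 = 2/1.035 + 4·4 = 17.93. Then SE² = (127.93 − 17.76)/50 = 2.203, SE = 1.484, and power = Φ(2.08) = 0.981.

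The other values are 0.9998 (k = 2), 0.918 (k = 6) and 0.833 (k = 8). The stated 95% is consistent with k up to about 4 to 5. Without k it cannot be reproduced exactly.

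**4. Shift in mean Total ABR from one dropout**

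With window W and time to exit t, the penalised mean is (49·2·W + 2t + 35(W − t))/(50W). The unpenalised mean is 2.00, so the shift is 33(W − t)/(50W). For exit on day d and cutoff on Day 455 this is 33·(455 − d)/(50·378).

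| Exit day | n = 50 | n = 70 (× 50/70) |
|---|---|---|
| 91 | 33·364/18,900 = 0.64 | 0.45 |
| 183 | 33·272/18,900 = 0.47 | 0.34 |
| 274 | 33·181/18,900 = 0.32 | 0.23 |
| 365 | 33·90/18,900 = 0.16 | 0.11 |

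- Solving the identity-link negative binomial estimating equation at k = 0, 1 and 4 gives the same n = 50 values.
- With a Day 730 cutoff the n = 50 shifts run from 0.37 (Day 365 exit) to 0.65 (Day 91 exit).
- A dropout with heavier bleeding before exit changes little. For 2.5 bleeds in 0.25 years, the mean goes from 103.93/50.97 = 2.04 to (103.93 + 35·0.785)/51.75 = 2.54, a shift of 0.50.
- The size depends on the penalty. For a Day 183 exit, 20.8/year (16.8 + 4, from Protocol 9.2) gives 0.27, and 47.6/year (the highest on-demand Total ABR in Protocol Table 3) gives 0.66.

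**5. Effect on decisions**

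The setting is 4,000 simulated trials of 50 paired participants with one Day 183 dropout and a Day 455 cutoff. The estimator is a pooled rate with a sandwich standard error, which approximates the SAP's GEE model.

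| k | NI success: truncated → penalised | Superiority success: truncated → penalised |
|---|---|---|
| 1 | 1.00 → 1.00 | 0.98 → 0.81 |
| 2 | 1.00 → 1.00 | 0.85 → 0.58 |
| 4 | 0.997 → 0.990 | 0.55 → 0.33 |

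Each Day 183 dropout moves the point difference by 0.475. About 3/0.475 = 6.3 of them would bring it from −3 to 0, and 6/0.475 = 12.6 would bring it to +3. With five, simulated NI success is 0.93, 0.77 and 0.53 at k = 1, 2 and 4.

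**The case against.** The strongest reply is that Table 11 states its dropout rule openly, and the SAP version history describes these analyses as aligned to regulatory requests. That correspondence is not public, so the agency may have wanted exactly this rule.

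The uncovered case is also narrow. Resumption is dated from the investigator's decision, not the first infusion (SAP 2.2.1). Prophylaxis-like use triggers the 35 without a recorded resumption. Failing participants may resume while staying on study (Protocol 6.5.1), and bleeds before exit still count. The treatment-failure listing in SAP 6.1.1.3 would bring such a case to clinical review. Finally, a penalty tied to a reason recorded in an open-label study is open to judgement.

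Most of this stands as a limit on size and frequency. It does not close the gap: the listing changes no estimate, and no other Total ABR analysis penalises the event.

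Three stronger readings are tempting, and the documents do not support them:

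- **A participant coded under another reason would escape the FVIII endpoint too.** The tested FVIII >5% endpoint fails every discontinuation before Month 15. The reason matters only for the geometric-mean and by-visit summaries, which carry no hypothesis test.
- **Protocol 7.2 shows that lack of efficacy cannot be recorded.** Its list is introduced as an inclusion and is not shown to be exhaustive. Protocol 10.9.5 refers to selectable discontinuation statuses and a field to specify them. The CRF itself is not available.
- **The primary analysis is inconsistent in the same way.** It truncates at resumption and at discontinuation alike, and says so.

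**Conclusion.** The gap is real and confined to the US-specific Total ABR analyses. One lack-of-efficacy dropout among 50 who is not covered by Table 10 lowers mean postinfusion Total ABR by about 0.16 to 0.64 bleeds/year for a Day 455 cutoff, depending on exit time. That is 8% to 32% of the assumed 2/year. With 70 dosed participants it is about 0.11 to 0.45.

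These sizes are relative to the SAP's own 35, so they do not show that the true rate is understated: bleeding after exit is unknown. A reader might also infer a threat to noninferiority. One dropout poses none. Several would be needed, the documents give no expected number, and Protocol 3 expects missing data to be rare.

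The chance of superiority in these analyses can fall noticeably, but the figures rest on assumed dispersion and on the 35. Because the analyses are outside the gatekeeping sequence (SAP Table 8), no gatekept test changes. This is a cheap improvement in consistency, not a defect in the primary analysis.

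**What to change.** - **Table 10:** add a third event, discontinuation for lack of efficacy with no prior resumption of prophylaxis, and assign a Total ABR of 35 from the discontinuation date to data cutoff.
- **Table 11, last intercurrent-event bullet:** extend the exception to discontinuation for lack of efficacy, alongside prior resumption.
- **Identification:** use the same lack-of-efficacy determination that SAP 3.2.4 and 3.2.5 already require, and confirm that the CRF captures it.

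If the sponsor prefers not to tie a fixed penalty to a recorded reason, a tipping-point analysis over the post-exit bleeding rate of such dropouts is the minimum alternative.

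The cost is one table row, one clause and a CRF check. If no such dropout occurs, no result changes. If one does, the US-specific estimate becomes slightly less favourable, and the penalty depends on a reason recorded in an open-label study. That is why the rule should be fixed before the data are analysed.
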